7.5.4 Adverse Events

For each adverse event, number and percent of eyes reported with the event will be summarized at each scheduled visit (including intraoperatively) and during the study (i.e. cumulative and persistent).

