cannula on a 5cc syringe filled with BSS to vigorously irrigate the space between the two lenses. If for some reason the vigorous irrigation did not remove all the debris from the inter-lenticular space carefully release the haptic/tabs of the IOPCL closest to the location of the debris and continue to irrigate. If this approach is unsuccessful consider removing the IOPCL, irrigate the surface debris on the surface of the IOL and replace it with another IOPCL. If the debris attached to the surface of the IOL remains adhered after the final attempt to irrigate do not introduce a new IOPCL. At the conclusion of the case, please record in detail on the CRF every and all steps taken to remove the cellular material between the two lenses.

REMOVAL OF THE IOPCL

Re-open the initial incisions or create new access into the anterior chamber if they have healed. With ProVisc in the anterior chamber use a Sinskey hook or similar instrument to disengage the three IOPCL haptics from their respective channels. Place a small amount of ProVisc between the IOPCL and existing PCIOL to separate them apart. Using microforceps thru the 2.0 mm wide incision, grasp the anterior and posterior surface of the IOPCL and remove it through the incision. The IOPCL is flexible and will fold and achieve a "taco" form for removal in one piece. After explantation of the complete IOPCL, assess the lens surface of the existing PCIOL for any damage. If any damage is noticed on the existing PCIOL particularly on its lens surface, please record this on the IOPCL removal Case Report Form. Remove the remaining ProVisc, irrigate and close the wound per your normal IOL procedures.

Please return the removed IOPCL to the Sponsor for damage assessment.

YAG CAPSULOTOMY

A Nd:YAG capsulotomy is not allowed to treat opacity between the IOPCL and PCIOL after implanting the IOPCL. Irrigation should be performed to remove the cellular matter from the lens(es) See page 10 for irrigation instructions

If clinically significant PCO is observed on the posterior side of the PCIOL, treatment using standard Nd:YAG capsulotomy is allowed. Nd: YAG capsulotomy should not be performed prior to 12 weeks post IOPCL implantation.

10. Examination Schedule

Subjects will be examined and evaluated according to the following schedule of visits.

Form OA – Pre-Operative Operative (Form OB)

Form 1 (1 to 2 days postoperative)

Form 2 (7-14 days postoperative)

Form 3 (30-60 days postoperative)

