10.1 Post-Explantation IOPCL Examination Schedule

Following the removal of the IOPCL subjects will be evaluated according to the following schedule of visits.

Form 1X (1-2 days post-removal)

Form 2X (7-14 days post-removal)

Form 3X (30-60 days post-removal)

Form 4X (120-180 days post-removal)

Form 5X (330-420 days post-removal)

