- ➤ Malpositioned/Misaligned Optics (IOPCL not centered over PCIOL)
 - o Early[1]
 - o Late[2]
- Unseated IOPCL haptic tabs (One or more haptic tabs not securely attached to the PCIOL)

- > Post Nd:YAG Posterior capsulotomy event
- > Lens Optical Performance
- Mechanical Failure
- Vitreous Aspiration for Pupillary Block
- Corneal Stroma Edema
 - Corneal Edema with BCDVA of 20/40 or worse at Form 3 (1-2M post-op) or later
- > Iritis present at 1-month or later
- Macular Edema present at 1-month or later
- > Raised IOP requiring treatment
 - Raised IOP, greater than 10 mmHg above baseline and to a minimum of 25 mmHg.
- ➤ Iris Chafing
- > Iris Trauma and/or Damage
- > Iris Transillumination Defects
- > Pigment Dispersion
- > Pseudophacodonesis or Evidence of Zonular Trauma/dehiscence
- > Inter-device opacification or fibrosis between the PCIOL and IOPCL
- > Other

```
[1]Early – prior to Form 4 visit window (i.e., < 120 days)
[2]Late – At 120 days or later
```

Note: Secondary Surgical Intervention(s) (SSI) may be necessary to resolve any of the adverse events identified above. If an SSI is conducted in the trial, the details of the SSI and corresponding reason for SSI will be documented on the SSI CRF.

Examples of Secondary Surgical Interventions

- ➤ Irrigation of IOPCL/IOL Interface
- > Exchange
- ➤ Reposition of the same Implantable Pseudophakic Contact Lens
- ➤ Removal

13. Adverse Experience and Complication Reporting

Throughout the course of the proposed study, all efforts will be made to remain alert to possible adverse experiences or untoward findings. If adverse experiences occur, the first concern will be the safety and welfare of the subject and appropriate medical intervention will be made. Any adverse experiences observed by the investigator or reported by the subjects, whether or not ascribed to the investigational procedure or device, will be recorded on the subjects' adverse event case report form. A new adverse event case report form is used for each adverse event or adverse event related visit.

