6 STATISTICAL CONSIDERATIONS

6.1 General Considerations

Descriptive statistics (mean, median, standard deviation, minimum, and maximum) will be used to summarize continuous variables. Frequencies and percentages will be used to summarize categorical variables.

Any analysis not described in this plan will be considered exploratory, and will be documented in the clinical study report (CSR) as a post hoc analysis or a change to the planned analysis.

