6.2 Sample Size

Sample size is limited to maximum of 10 subjects (eyes) for this Early Feasibility Study (EFS).

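### The SAP has no summary of lens irrigation, exchange, repositioning or removal and no rule for post-removal data, so an eye explanted early drops out of the adherence percentage without counting as a failure

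*SAP*

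**What the plan says.** **Protocol, section 12.** After the intraoperative and postoperative adverse-event lists, a note says "Secondary Surgical Intervention(s) (SSI) may be necessary to resolve any of the adverse events identified above", and that "the details of the SSI and corresponding reason for SSI will be documented on the SSI CRF". Four examples follow: irrigation of the interface between the lenses, exchange, removal, and "Reposition of the same Implantable Pseudophakic Contact Lens".

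**Protocol, section 9, removal instructions.** If the existing IOL (PCIOL) is found damaged at explantation, the surgeon is told "please record this on the IOPCL removal Case Report Form".

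**Protocol, sections 10.1 and 11.** "Following the removal of the IOPCL subjects will be evaluated according to the following schedule of visits": five visits, Forms 1X to 5X. They collect acuity, refraction, slit-lamp findings, gonioscopy, pressure, QoV and adverse events. UBM is scheduled at 30-60, 120-180 and 330-420 days and at interim visits, with no post-removal entry. Section 15.4.1 counts post-removal examinations towards study completion.

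**SAP.** Section 7.5.4 says "For each adverse event, number and percent of eyes reported with the event will be summarized at each scheduled visit (including intraoperatively", and also over the study. Section 7.5.3 reports, from observed data, the share of eyes whose lens gap changes by no more than 10 microns between 1-2 and 4-6 months. Sections 6.5 and 7.5 rule out imputation. Section 5 takes in every eye in which implantation was attempted. Section 6.2 states "Sample size is limited to maximum of 10 subjects (eyes) for this Early Feasibility Study (EFS". Under section 6.1, "Any analysis not described in this plan will be considered exploratory".

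**The concern.** The primary objective in both documents is that the lens stays attached without rotation or slippage. For such a device, a second operation to reposition, replace or remove it bears directly on that objective. The protocol provides for recording these operations, but the SAP gives them no place in the results.

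Three things follow:

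- The planned tables can show an event such as a malpositioned lens or an unseated tab without showing that the eye was reoperated on for it.
- Post-removal data have no stated destination.
- The adherence percentage can lose the eyes whose lens was taken out and keep eyes whose lens was moved or replaced.

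SAP section 4 ties an IDE application to outcomes once all eyes have had the chance to reach the 4-6 month visit, which is when the adherence result is read. A count of reoperations added later would carry the exploratory label of SAP 6.1.

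**Working it through.** The plan has no figure to reproduce: the sample size is a cap of 10 with no formula. The check is a comparison of the two documents, followed by arithmetic on assumed counts.

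**1. Are the four interventions tabulated anywhere?**

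| Intervention | In the adverse-event lists? | Recorded on | SAP section reporting it |
|---|---|---|---|
| Irrigation | No | SSI form | None |
| Exchange | No | SSI form | None |
| Repositioning | No | SSI form | None |
| Removal | No | SSI form and removal form | None |

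All four are outside the lists. SAP 7.5.1 to 7.5.5 mention none of them, nor PCIOL damage found at removal. SAP 7.1 summarises reasons for discontinuation, but an explanted subject remains in follow-up (Protocol 10.1 and 15.4.1), so removal need not appear there.

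**2. Where do post-removal data go?** Forms 1X to 5X use the same day windows as Forms 1 to 5, counted from removal. SAP 6.4 counts postoperative days from implantation. If removal is on day d, Form 3X falls between days d + 30 and d + 60. That range lies wholly inside the Form 4 window of 120-180 days when d is at least 120 - 30 = 90 and at most 180 - 60 = 120. A post-removal visit could therefore enter a lens-in-place summary either through its nominal label or through its postoperative day. It could equally be left out. The SAP does not decide.

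**3. What happens to the adherence percentage?** An eye explanted before 4-6 months has no second UBM gap. With observed data and no imputation, it leaves both numerator and denominator. Let k of 10 eyes be explanted before that visit and the remaining 10 - k be stable. The counts are assumptions, since the documents give no SSI rate.

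| k | Observed-data result, (10 - k)/(10 - k) | Over all attempted eyes, (10 - k)/10 |
|---|---|---|
| 0 | 10/10 = 100% | 10/10 = 100% |
| 1 | 9/9 = 100% | 9/10 = 90% |
| 2 | 8/8 = 100% | 8/10 = 80% |
| 3 | 7/7 = 100% | 7/10 = 70% |

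The reported result does not move as removals accumulate.

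**4. Repositioned or exchanged lenses.** SAP 7.5.3 does not require the lens to be the original one or to have been left undisturbed. If the lens is repositioned or replaced before the 1-2 month scan, both scans describe the position after that surgery. A difference within 10 microns then counts as stable. The adverse-event table may show the triggering event, but no planned result says that the stable lens had been moved or replaced.

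**5. Precision and chance of occurrence at n = 10.** Exact (Clopper-Pearson) 95% intervals for an SSI proportion:

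- 0/10: 0 to 30.8%
- 1/10: 0.3 to 44.5%
- 2/10: 2.5 to 55.6%

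The chance of at least one SSI is 1 - (1 - p)^10. For assumed true rates of 5, 10, 20 and 30% it is 40.1, 65.1, 89.3 and 97.2%.

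**The case against.** The strongest reply is that this is a small, unmasked, descriptive feasibility study with no decision rule resting on SSIs. A listing could be added by amendment before database lock, and SAP 6.1 would only attach a label to it. That is fair, and it is why the point is a cheap improvement and no more. It does not answer the adherence percentage, which is a planned result and can mislead without the listing.

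Four stronger readings are tempting, and the documents do not support them:

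- *The safety analysis covers only the adverse-event list.* That is true of SAP 7.5.4 alone. Section 7.5 also covers acuity loss, delivery, UBM stability, acuity by visit, pressure, slit-lamp and fundus findings, and QoV.
- *No secondary surgery is counted at all.* Vitrectomy, and iridectomy and vitreous aspiration for pupillary block, are listed adverse events and would be tabulated. The gap concerns the four named SSIs.
- *Nothing after removal is reported.* Post-removal adverse events are collected and fall within the cumulative count. SAP 5 does not exclude explanted eyes, and the by-visit wording in SAP 7.5.5.1 could be read to include the X visits. The defect is undefined handling, not demonstrated absence.
- *Explanted eyes are necessarily the worst outcomes.* No rule in the documents links removal to worst outcome.

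The case report forms and the ISO accountability tables invoked in SAP 7.1 are not available here, so some linkage between SSI and adverse-event records may exist on the forms. The SAP text does not provide for an analysis of it.

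**Conclusion.** The concern stands in this form: the four named SSIs have no planned summary, post-removal data have no stated handling, and the adherence percentage can omit explanted eyes and count repositioned or exchanged lenses as stable. On the illustrative counts of 2 early removals and 8 stable eyes, the plan reports 100% where 80% of attempted eyes still have a stable lens in place, a gap of 20 percentage points. Each further early removal adds 10 points.

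This assumes 10 attempted eyes, removal before the 4-6 month scan, and a denominator of eyes with both scans. That denominator is the natural reading of observed data without imputation, although SAP 7.5.3 does not spell it out. If no SSI occurs, none of the planned results changes. It is a cheap improvement.

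**What to change.** In SAP 3.2, 7.5.3 and 7.5.4, add the following over all eyes in which implantation was attempted:

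- (a) n/N eyes with any SSI and with each type, with day and reason. At 10 eyes or fewer a listing is enough; an exact interval for any SSI is optional.
- (b) n/N eyes with the original lens in place and no SSI at 4-6 and 12 months, shown beside the UBM stability result.
- (c) Any PCIOL damage found at removal.
- (d) A statement that lens-in-place by-visit summaries exclude post-removal visits. For each explanted eye, list separately the BCDVA change from preoperative and the IOP at the Form 1X to 5X visits where each is scheduled.

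The cost is one SAP paragraph and one extra table or listing, from forms the protocol already provides. The downside is a less favourable summary if secondary surgery occurs. Making the change before database lock, as SAP section 1 allows, avoids the post hoc label.

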7.5.5 Other Safety Analyses

7.5.5.1 Best-corrected Distance Visual Acuity

All the available monocular best-corrected distance visual acuity at each protocol specified scheduled visit will be presented for the primary eyes. The categorical presentations will include the visual acuity of 20/16 or better, 20/20 or better, 20/25 or better, 20/32 or better, 20/40 or better, 20/50 or better, 20/63 or better, 20/80 or better, and worse than 20/80.

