- 3. Willing and able to complete all required postoperative visits.
- 4. Subjects who's baseline MRSE is between -0.5D and +3.0D
- 5. Best corrected visual acuity 20/80 or worse.
- 6. Subjects with $\leq 1.5D$ of corneal cylinder
- 7. Subjects willing to abstain from pursuing any other surgical vision-correcting procedures for the duration of the study.
- 8. Subject must be at least 22 years or older.

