3.1.2 Additional Effectiveness Outcomes

Other important effectiveness outcomes include the following visual acuity measurement:

Monocular uncorrected distance visual acuity (UCDVA)

These effectiveness outcomes will be summarized descriptively for different lens groups. The differences between preoperative and postoperative results will also be summarized by descriptive statistics. The 95% confidence intervals of mean difference may be provided.

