7.4.2 Additional Effectiveness Analyses

The analysis in section 7.4.1 will be repeated using auto-refraction instead of MRSE for an objective understanding of the change in refraction as this study includes patients with underlying pathology with poor BCDVA, which can impact the reliability of MRSE measurements.

All the available monocular uncorrected distance visual acuity at each protocol specified scheduled visit will be presented for the primary eyes. The categorical presentations will include the visual acuity of 20/16 or better, 20/20 or better, 20/25 or better, 20/32 or better, 20/40 or better, 20/50 or better, 20/63 or better, 20/80 or better, and worse than 20/80.

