7.5.1 Preservation of BCDVA

The analysis of this clinical outcome will be based on the observed data of AccuraSee IOPCL. The number and percent of IOPCL implanted eyes with a BCDVA loss of 2 or more lines from preoperative will be derived.

Additionally, if needed, data listing or summary will be provided for eyes with a BCDVA loss of ≥ 2 lines from the best BCDVA before the corresponding visits.

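### The BCDVA classes in SAP 7.5.5.1 do not separate acuities worse than 20/80, where every eligible baseline level except exactly 20/80 lies, and the corneal edema acuity limit is already met before surgery

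*SAP*

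**What the plan says.** Protocol 3.1, item 5, sets the entry level: "Best corrected visual acuity 20/80 or worse". No lower limit is given. The SAP recognises this population; section 7.4.2 notes that "this study includes patients with underlying pathology with poor BCDVA".

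SAP 7.5.5.1 starts broadly: "All the available monocular best-corrected distance visual acuity at each protocol specified scheduled visit will be presented for the primary eyes". It then names nine classes. Eight are cumulative, from 20/16 to 20/80, and the ninth is open; the list closes with "20/63 or better, 20/80 or better, and worse than 20/80". The list is introduced as what the presentation will include, so it is not closed.

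Three other provisions bear on BCDVA:
- SAP 7.5.1: "The number and percent of IOPCL implanted eyes with a BCDVA loss of 2 or more lines from preoperative will be derived". If needed, it adds a listing or summary of losses of two or more lines from the best earlier BCDVA.
- SAP 6.1: "Descriptive statistics (mean, median, standard deviation, minimum, and maximum) will be used to summarize continuous variables". This is generic and does not mention BCDVA change.
- SAP 3.1.2: "The differences between preoperative and postoperative results will also be summarized by descriptive statistics". The only outcome listed there is UCDVA. Sections 7.5.5.2 and 7.5.5.4 name a change from baseline for IOP and QoV.

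In Protocol section 12, the corneal stroma edema event has a sub-item for edema at Form 3 or later with BCDVA at 20/40 or below. That limit is an absolute level, not a change.

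**The concern.** The class list resolves acuities that no eligible eye can have at baseline and lumps together nearly all those it can have. The categorical BCDVA table is therefore least informative in the range where this study's eyes start.

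The only change output named without condition is a yes/no count of losses. It gives neither the size of a loss nor any gain. The size and direction of change from a poor starting level are of interest here, and the SAP names change summaries for UCDVA, IOP and QoV but not for BCDVA.

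The corneal edema sub-item has a related fault. A fixed limit of 20/40 can mark visual impact in eyes that start with good acuity. In eyes that start at 20/80 or below, it mostly reflects vision that was poor beforehand.

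**Working it through.** The documents give no derived figure on this point, so there is none to reproduce. The check maps eligible acuities onto the named classes.

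**Inputs.** Eligible baseline: 20/80 or lower (Protocol 3.1, item 5). Classes: SAP 7.5.5.1. Edema limit: 20/40 (Protocol section 12).

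**Assumption.** One line = 0.1 logMAR. The text at hand does not define a line, and Appendix 3 (clinical methods) is only listed in it. The SAP's own classes fit the assumption: log10(63/50) = 0.100 and log10(80/63) = 0.104.

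**Formulas.** logMAR = log10(denominator / 20); lines between two levels = difference in logMAR / 0.1.

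**Step 1: classes at baseline.** Of the nine classes, the seven from 20/16 to 20/63 are empty for any eye that meets item 5. An eye at exactly 20/80 falls in the eighth. Every lower level falls in the ninth, open class.

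**Step 2: gains.** The baseline distribution is not given, so a range of starting levels is shown. An eye in the open class changes class only when it reaches 20/80 (logMAR 0.602). It stops meeting the 20/40 limit only when it reaches the next better step, 20/32 (logMAR 0.204).

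| Start | logMAR | Lines to reach 20/80 | Lines to reach 20/32 |
|---|---|---|---|
| 20/80 | 0.602 | 0 (already there) | 3.98 |
| 20/100 | 0.699 | 0.97 | 4.95 |
| 20/125 | 0.796 | 1.94 | 5.92 |
| 20/160 | 0.903 | 3.01 | 6.99 |
| 20/200 | 1.000 | 3.98 | 7.96 |
| 20/400 | 1.301 | 6.99 | 10.97 |

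For example, a gain from 20/200 to 20/100 is (1.000 − 0.699) / 0.1 = 3.01 lines and leaves the class unchanged. A one-line gain from 20/100 to 20/80 does show.

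**Step 3: losses.** A loss from 20/80 moves the eye into the open class and shows. Losses from lower levels do not:
- 20/100 to 20/160: (0.903 − 0.699) / 0.1 = 2.04 lines, same class.
- 20/200 to 20/320: (1.204 − 1.000) / 0.1 = 2.04 lines, same class.
- 20/100 to 20/400: (1.301 − 0.699) / 0.1 = 6.02 lines, same class.

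The count in SAP 7.5.1 catches all three, each as one affected eye. The 2-line and 6-line losses look alike there, and gains do not appear.

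**Step 4: edema limit.** 20/40 is logMAR 0.301. The best eligible eye is (0.602 − 0.301) / 0.1 = 3.01 lines worse. Every eligible eye therefore meets the acuity part before surgery, and goes on meeting it unless it gains the lines in the last column of the table (about 4 from 20/80, about 11 from 20/400). An eligible eye with late corneal edema and unchanged vision is placed in the sub-item just like one whose vision fell.

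**The case against.** The strongest reply is that the safety question is already answered. SAP 7.5.1 and the safety endpoint count losses of two or more lines from preoperative at any acuity level, so each loss in the working is captured. SAP 7.5.5.1 presents all available BCDVA, its class list is open to additions, and with at most 10 eyes each eye's course could be read from a listing. Empty upper classes at baseline cost nothing and can show postoperative gains past 20/80. Corneal edema sits under a parent event, all events are summarised by visit (SAP 7.5.4), and BCDVA is scheduled at the same late visits, so the two can be read together.

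Most of this stands, and it rules out several stronger readings. A reader might infer that the SAP names no BCDVA change summary at all; 7.5.1 names one. A reader might infer that vision loss from a poor baseline would go unseen; it would be counted. A reader might infer that every eligible eye is in the open class; one at exactly 20/80 is not. A reader might infer that the edema event is met before surgery or that events are lost; edema at Form 3 or later is still required, and the limit over-labels rather than hides.

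What the reply does not supply is a named summary of the size or direction of BCDVA change. SAP 7.5.5.1 does not say that its presentation will be by eye, the further output in 7.5.1 is conditional and confined to losses, and 6.1 is generic. Nor does it give the edema limit any power to discriminate in this population.

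**Conclusion.** The point holds as a minor reporting improvement in a descriptive study of at most 10 eyes. For eligible eyes starting worse than 20/80, the named BCDVA classes cannot show a further loss, or a gain that stays below 20/80. Changes of 2 to 6 lines can leave the class unchanged. No gain category, line-change distribution or mean change in BCDVA is named. The acuity part of the corneal edema sub-item is met before surgery by every eligible eye.

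The statements about class membership and the edema limit need only item 5 and the listed classes. The line counts rest on the assumed 0.1 logMAR step, and how many eyes are affected depends on a baseline distribution that the documents do not give. All of this concerns eyes that meet item 5; an eye entered under an exemption (SAP 7.3 allows for these) could start better.

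The cystoid macular edema item in Protocol section 12 can be read as a level of 20/40 or as a reduction of unstated size. That is wording to reconcile, with no effect shown here. No endpoint or stopping rule changes.

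**What to change.** 1. In SAP 7.5.5.1, keep the existing classes and add some below 20/80, for example 20/100, 20/125, 20/160, 20/200, 20/400 and worse.
2. In the same section, name a line-change or shift table from preoperative, by visit, covering gains as well as losses. List separately any eye that cannot read the chart, since item 5 has no lower limit.
3. In the analysis, also tabulate late corneal edema by BCDVA change from preoperative, for example using the two-line loss already in the safety endpoint. Keep the 20/40 version as a listing.
4. Reconcile the cystoid macular edema wording so that it reads clearly as a level or as a change.

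The cost is a few table shells and one added tabulation. No new measurement is needed, because Protocol section 11 already schedules BCDVA preoperatively and from the 7-14 day visit on. The drawback is that baseline-relative edema counts may be lower than the 20/40 counts and not directly comparable with them, which is why the 20/40 listing should stay.
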